2.3 Rationale

2.3.1 Rationale for conducting the study

Once prostate cancer (PCa) metastasizes it is incurable and advanced PCa continues to kill more than 27,000 men per year in the United States (1). Yet, localized prostate cancer is often curable and even metastatic disease can respond to treatment.

PCa cells exist in a complex habitat within their microenvironment, co-existing with other normal host cells, including hematopoietic precursors, stromal cells, osteoblasts, osteoclasts, nerve cells, adipocytes, endothelial cells, and multiple cell types of the immune system including macrophages (2). Within the ecosystem of the tumor, these host cells provide the cancer cells with a multitude of growth factors and cytokines that result in tumor promotion and growth. In turn, the cancer cells provide growth factors to the host cells that result in their proliferation and survival. Disruption of this cooperation is a paradigm that could be explored and exploited as a way to suppress tumorigenesis and overall, eradicate tumors both at primary and metastatic sites.

Malignant tumors are associated with a leukocytic infiltrate as part of the reactive stroma that is enriched for macrophages (2-10). Macrophages play an important role in the regulation of angiogenesis in both normal and diseased tissues, including malignant tumors (2-10). It is not clear whether TAMs are derived from peripheral blood monocytes recruited into the tumor from the circulation or from resident macrophages already in the healthy tissue before tumor develops and metastasizes. However, elevated expression of a number of monocyte chemoattractants, including chemokines CCL2, CCL3, CCL4, CCL8 and CCL5 (RANTES) by both tumor and stromal cells within the tumor microenvironment has been shown to positively correlate with increased M2-TAM recruitment within several human tumor types (2-10, 15-20). When associated with tumors, macrophages demonstrate functional "polarization" towards one of two phenotypically different subsets of macrophages: $T_{H}1$ (also known as M1 macrophages) or T_{H2} (also known as M2 macrophages). M1 macrophages are known to produce proinflammatory cytokines and play an active role in cell destruction. Conversely, M2 macrophages primarily scavenge debris and promote angiogenesis and wound repair (2-10, 15-20). The M2 macrophage population is phenotypically similar to the TAM population that promotes tumor growth and development. Others and we have demonstrated the importance of TAMs in promoting PCa tumorigenesis. TAMs have been demonstrated to make up to 50% of the population of cells in PCa bone metastases, contributing to cancer cell growth by promoting a permissive growth environment through the secretion of matrix degrading enzymes, angiogenic factors such as VEGF, and multiple growth factors while simultaneously secreting multiple factors that suppress the host immune response (15-20).

We have demonstrated that Inhibition of IL-4 by blocking IL4r α blocks polarization to the M2 phenotype and significantly inhibits prostate tumor growth. Human macrophages were polarized using phased polarization protocol, each conditi in triplicate (21). On day 5, 10 ng /mL of the anti-IL4r α antibody Dupilumab was added to the cultures. On day 9, % of cells exhibiting CD206 and CD163 as markers of M2 polarization was determined by FACS sorting per published protocol (**Table 2**). We next tested the ability of IL4r α inhibition to inhibit tumor growth *in vivo* in preclinical mouse models. Parallel studies

were conducted in human SCID mice using the human cell line PC3 as well as the Hi-Myc B6CaP model. For the PC-3 model, 500,000 cells were implanted into mice (n=12 per group). When these tumors reached 2mm³ (week 2), animals began treatment. Docetaxel was given as a single dose of 5mg/kg at week 2 per published protocol (22-27). Mice were treated weekly (weeks 2,3,4,5,6) with a murine specific anti-IL4r α antibody (rat anti-mouse IL-4R alpha clone 129801 (R&D Systems MAB530) since Dupilumab is human specific. Tumor growth was measured weekly with caliper measurements. As single agents, both docetaxel and anti-IL4r α antibody inhibited tumor growth by 33% (p<0.05). The combination of docetaxel + anti-IL4r α antibody inhibited tumor growth by 75% (p<0.01). At week 7, tumors were excised and FACS analysis was performed to determine the number of CD68+ macrophages as a percent of cellular mass as per published protocol (27). IL4r α inhibition significantly decreased macrophage infiltration into the tumor mass as compared to control and docetaxel treated alone tumors, p<0.001. Similar significant results were demonstrated utilizing the Hi-MYC mouse model (results not shown).

2.3.2 Rationale for dosage selection

In the Phase III studies utilizing DUPILUMAB the prescribed dosage proposed in this trial was considered to be the safe and effective dose. Specifically, a third randomized treatment arm of DUPILUMAB 300 mg QW did not demonstrate additional treatment benefit over DUPILUMAB 300 mg Q2W (11,12)

2.3.3 Rationale for immunobiologic endpoints

The major efficacy goal of this study is to assess a decrease in M2-TAM infiltration in tumors based on our preliminary data. To do this, we have developed a CD206 antibody for immunohistochemical analysis (IHC) and demonstration of M2-TAM infiltration into primary and metastatic prostate cancers. The analysis of M2-TAM infiltration into human tumors has previously not been possible because of lack of a specific marker for M2 macrophages. Current markers, e.g., CD68, are specific for all human macrophages but do not reflect polarization states. Working with our collaborator [name], Director of the Tissue Core for the Sidney Kimmel Cancer Center (SKCCC) at Johns Hopkins School of Medicine, utilizing stringent protocols to assess and quantify antibody staining, we have developed an anti-CD206 reagent to allow staining of human tissue microarrays to assess M2-TAM infiltration (28, 29, and submitted). Utilizing this antibody, we have demonstrated a significant increase in M2-TAMs in prostate tumors compared to normal tissue.

We will also quantify the extent of CD8+ T cell and CD4+ T cell infiltration into the prostate from harvested prostate glands of treated patients. We will quantify markers of apoptosis in prostate tumor specimens of treated patients using TUNEL staining and expressed as the mean staining percentage in tumor tissue and quantify markers of cell proliferation in prostate tumor specimens of treated patients using Ki-67 staining and expressed by the mean staining percentage in tumor. We will evaluate the proportion of pathological complete responses in prostate tumor specimens of treated patients who achieve an undetectable PSA (<0.1 ng/mL) by 2 months after prostatectomy.

3. Patient Selection

3.1 **Target Population**

Subjects will include men with multifocal, Gleason 7 or greater, clinically localized prostate cancer (NCCN High Risk / Very High Risk) for whom the decision has been made to perform radical prostatectomy at Johns Hopkins Hospital. Subjects will be identified and recruited through the Outpatient Clinic of the Department of Urology and from the Multidisciplinary Prostate Cancer Clinic.

3.2 **Inclusion Criteria**

To be eligible for this study, patients must meet *all* of the following criteria:

- Histologically confirmed adenocarcinoma of the prostate (clinical stage T1c–T3b. • N0, M0) without involvement of lymph nodes, bone, or visceral organs
- Initial prostate biopsy is available for central pathologic review, and is confirmed • to show at least 2 positive cores and a Gleason sum of ≥7
- Radical prostatectomy has been scheduled at Johns Hopkins Hospital •
- Age ≥18 years •
- ECOG performance status 0-1. or Karnofsky score \geq 70% (see Appendix A) •
- Adequate bone marrow, hepatic, and renal function:
 - WBC >3,000 cells/mm³
 - \circ ANC >1,500 cells/mm³
 - Hemoglobin >9.0 g/dL
 - Platelet count >100,000 cells/mm³
 - \circ Serum creatinine <3 × upper limit of normal (ULN)
 - Serum bilirubin <3 × ULN
 - \circ ALT <5 × ULN
 - AST <5 × ULN
 - Alkaline phosphatase <5 × ULN
- Willingness to provide written informed consent and HIPAA authorization for the • release of personal health information, and the ability to comply with the study requirements (note: HIPAA authorization will be included in the informed consent)
- Willingness to use barrier contraception from the time of first dose of • DUPILUMAB until the time of prostatectomy.

3.3 **Exclusion Criteria**

To be eligible for this study, patients should *not* meet *any* of the following criteria:

- Presence of known lymph node involvement or distant metastases
- Other histologic types of prostate cancers such as ductal, sarcomatous, lymphoma, small cell, and neuroendocrine tumors
- Prior radiation therapy, hormonal therapy, biologic therapy, or chemotherapy for • prostate cancer
- Prior immunotherapy/vaccine therapy for prostate cancer
- Concomitant treatment with other hormonal therapy or 5α -reductase inhibitors •

- Current use of systemic corticosteroids or use of corticosteroids within 4 weeks of enrollment (inhaled corticosteroids for asthma or COPD are permitted)
- Use of experimental agents for prostate cancer within the past 3 months from time of screening
- History or presence of autoimmune disease requiring systemic immunosuppression (including but not limited to: inflammatory bowel disease, systemic lupus erythematosus, vasculitis, rheumatoid arthritis, scleroderma, multiple sclerosis, hemolytic anemia, Sjögren syndrome, and sarcoidosis)
- History of malignancy within the last 3 years, with the exception of nonmelanoma skin cancers and superficial bladder cancer
- Uncontrolled major active infectious, cardiovascular, pulmonary, hematologic, or psychiatric illnesses that would make the patient a poor study candidate
- Known prior or current history of HIV and/or hepatitis B/C
- Significant eye disease

3.4 Inclusion of Minorities

Men of all races and ethnic groups will be considered for study participation. Candidates must conform to all eligibility criteria to be accepted into the study. Minority patients who meet entry criteria will be actively recruited, although the trial is not designed to measure differences in outcomes between ethnic groups. The estimated breakdown of the target population by race and ethnicity is: 80% white/Caucasian, 15% black/African American, and 5% comprised of other ethnic minorities.

3.5 Prohibited Concomitant Medications

Concurrent use of other anticancer agents or therapies including other experimental treatments is not permitted. Patients may not currently be taking any other form of androgen deprivation therapy, antiandrogens, 5⁻-reductase inhibitors, chemotherapy, radiation therapy, biologic therapy, immunosuppressive medications, or systemic corticosteroids.

Within 30 days of administration of study drug, patients should not receive vaccines including but not limited to the live rotavirus vaccine, the live BCG (bacillus Calmette-Guerin) vaccine, the live influenza vaccine, the live measles vaccine, the live mumps vaccine, the live poliovirus vaccine, the live rubella vaccine, the smallpox vaccine, the typhoid vaccine, the varicella vaccine, and the yellow fever vaccine.

Because of the potential for unknown drug-drug interactions, concurrent use of all other agents, over-the-counter medications, herbal remedies, vitamins/minerals, and alternative therapies must be documented on the case report form (CRF).

4. REGISTRATION AND ENROLLMENT PLAN

4.1 Registration Procedure

Patients who are considered candidates for the study will first be evaluated for eligibility by one of the principal investigators, co-investigators, or the research nurse. After screening for eligibility, patients who are eligible to participate in the trial must be registered with the Sidney Kimmel Comprehensive Cancer Center (SKCCC) according to the instructions below. A record of patients who fail to meet entry criteria (*i.e.*, screen failures) will also be maintained. Registration must be completed before beginning any study-related activities.

Once eligibility is confirmed, each subject will be assigned a unique patient study identification number. Treatment must not commence until the patient has received his identification number.

Prior to protocol enrollment and initiation of treatment, subjects must sign and date an IRB-approved consent form. Authorized study personnel should fully explain the scope of the study to each patient before obtaining informed consent. Patients should be advised of any known risks inherent in the planned treatments/procedures, any alternative treatment options, their right to withdraw from the study at any time and for any reason, and their right to privacy. When obtaining informed consent, study personnel should: **first**, confirm that the patient has received and has had time to read the informed consent form (including the research authorization/HIPAA form); **next**, confirm eligibility as defined in Sections 3.2 and 3.3 (inclusion and exclusion criteria); and **finally**, obtain dated and signed informed consent. A copy of the signed informed consent should be supplied to the study coordinator.

4.2 Expected Enrollment

A total of 20 patients will be included in this study. The first patients are expected to be enrolled in August 2018, once the protocol has been approved by the IRB. With an estimated enrollment rate of 2-3 patients per month, accrual is expected to be completed in 10 months.

4.3 Study Centers

This is a single-institution study that will be conducted only at Johns Hopkins through a collaboration between the Brady Urological Institute and the Sidney Kimmel Comprehensive Cancer Center.

4.4 Recruitment

Subjects will be recruited from the outpatient facilities of the Brady Urological Institute, and from the outpatient Multidisciplinary Prostate Cancer Clinic of the SKCCC. Patients will not receive payment or reimbursement for participation. Every effort will be made to include patients of racial and ethnic minorities who fulfill the eligibility criteria.

5. STUDY PLAN

5.1 Overview and Schema

This is a single-center, single arm, open-label phase II study evaluating the safety, antitumor effect, and immunogenicity of neoadjuvant DUPILUMAB given prior to radical prostatectomy in men with high-risk localized prostate cancer. Patients will be recruited from the outpatient Urology clinic. Men will be treated with dupilumab 600 mg s.q. on day 1, and then 300 mg s.q. on days 8, 15, 22, 29, 36, 43. They will then undergo surgery on day 57. 14 days after the last dose of Dupilumab, prostate glands will be harvested at the time of radical prostatectomy, and prostate tissue will be examined for the secondary endpoints. Follow-up evaluation for adverse events will occur 30 days and 60 days after surgery. Patients will then be followed by their urologists according to standard institutional practices, but will require PSA evaluations every 3 (\pm 1) months during year 1 and every 6 (\pm 2) months during years 2-3.

Table 1STUDY CALENDAR

Every effort should be made to keep visits, tests, and procedures on schedule. Acceptable deviations are listed below.

	Screening Evaluationª	Treatment Days (1, 8,15, 22, 29, 36, 43) (+/- 1 day)	Radical Prostatectomy Day 57 (+/- 3 days)	Follow-up, 30, and 60 Days Post-op (+/- 1 wk) ^{h,i}	LTFU (+/- 1 Month) ⁱ
Informed consent	Х				
Medical history	Х				
Review of medications	Х	Х	х	х	
Physical examination	Х	Х			
Vital signs	Х	Х	х		
Height and weight	Х	Х	х		
Performance status	Х	Х	х	х	
CT and bone scan ^b	(X)				
Hematology labs, coagulations ^c	х	х	Х	х	
Chemistry labs ^d	Х	Х	х	Х	
Serum PSA ^e	Х		х	Х	Х
DUPILUMAB dose		Х			
Toxicity assessment	X			X	
Surgical specimen ^f			Х		
Pathologic review ^g	Х		Х		

a: The screening (pre-treatment) evaluation should be conducted within 42 days (±4 days) of starting protocol therapy.

b: Staging CT (if allergic to CT scan contrast, obtain MRI with contrast) and bone scans should only be performed if clinically indicated, and are not mandatory.

c: Hematology laboratories include hemoglobin, hematocrit, white blood cell count with differential (including absolute eosinophil count), and platelets. In addition, prothrombin time (PT/INR) and activated partial thromboplastin time (APTT) should be checked at screening, then as clinically indicated.

d: Chemistry laboratories include sodium, potassium, chloride, bicarbonate, urea nitrogen, creatinine, glucose, calcium, albumin, total protein, bilirubin, alanine aminotransferase (ALT), aspartate aminotransferase (AST), and alkaline phosphatase.

e: Serum PSA should be obtained pre-treatment and on the day of surgery, and as clinically indicated thereafter according to institutional practices.

f: Harvested prostate gland to be evaluated for tumor apoptosis, CD8+ T cell infiltration, as well as other secondary endpoints.

g: Archival prostate core biopsies to be centrally reviewed at baseline prior to study entry; radical prostatectomy specimens to be processed at Johns Hopkins according to standard procedures.

h: The post-operative evaluations (30 and 60 days after prostatectomy) may take place over the telephone or in person, but patients are required to have hematology and chemistry labs collected at this time-point for safety purposes.

i: PSA should be measured every 3 months (±1 month) in the first year after prostatectomy, and every 6 months (±2 months) in the second and third years after prostatectomy.

5.2 Screening/Pretreatment Evaluation

Before initiating any screening activities, the scope of the study should be explained to each patient. Patients should be advised of any known risks inherent in the planned procedures, any alternative treatment options, their right to withdraw from the study at any time and for any reason, and their right to privacy. After this explanation, patients should be asked to sign and date an IRB-approved informed consent form that meets the requirements of the Code of Federal Regulations (Federal Register Vol. 46, No. 17, January 27, 1981, part 50).

The pretreatment/screening visit will determine patient eligibility according to the inclusion and exclusion criteria. All subjects must undergo a number of baseline evaluations as part of this screening visit, as detailed below. All of these evaluations should be conducted within 21 ± 4 days of starting the protocol. This information is also summarized in the Study Calendar (Table 1).

- informed consent
- demographic information
- medical history, including review of systems
- performance status, using ECOG or Karnofsky scales (Appendix A)
- physical examination
- vital signs: temperature, pulse, sitting blood pressure, respiratory rate
- height and weight
- current medication list, including drug allergies/adverse events
- hematological laboratories (hemoglobin, hematocrit, white blood cell count with differential [including absolute eosinophil count], platelets); coagulation profile (INR, aPTT) if clinically indicated
- serum chemistry profile (sodium, potassium, chloride, bicarbonate, urea, creatinine, glucose, calcium, albumin, total protein, bilirubin, ALT, AST, alkaline phosphatase)
- serum PSA level
- CT (If allergic to CT scan contrast, obtain MRI with contrast) and/or bone scan, only if clinically indicated (not mandatory)
- central pathologic review of prostate core biopsies

After all relevant screening information is documented, registration should be finalized and appropriate documents (*i.e.*, signed informed consent, supporting source documentation for eligibility) should be faxed or emailed to the program manager.

Information on patients who do not meet eligibility criteria to participate in this study (*i.e.*, screening failures) should also be captured at the pretreatment visit.

5.3 Treatment Visits

The following must be performed on treatment days (days 1, 8,15, 22, 29, 36, 43) (±1 day) with administration of DUPILUMAB.

• performance status

- review of medication list
- review of toxicity/adverse events
- height/weight
- vital signs (before and 1 hour post subcutaneous injection (which is at the end of a 1 hour observation period)
- physical exam (focused)
- hematological laboratories and serum chemistry profile
- Administration of DUPILUMAB (see section 6.3 Study Drug Administration)

5.4 Radical Prostatectomy

The following must be performed on the day of radical prostatectomy, which itself should occur 56 (± 3) days after the administration of first dose of DUPILUMAB.

- medical history
- performance status
- physical examination, including vital signs
- review of medication list
- review of toxicity/adverse events
- hematological laboratories and serum chemistry profile
- serum PSA
- collection of prostatectomy tissue for analysis of study endpoints
- pathological processing of prostatectomy specimen according to standard procedures

5.5 Follow-Up Evaluations

Follow-up visit scheduled for 30 days and 60 days after radical prostatectomy may occur in the outpatient clinic or by telephone interview. Required evaluations during this follow-up visits are listed below. Patients should then continue to be followed by their treating urologist according to standard institutional practices.

- performance status
- review of medication list
- review of toxicity/adverse events

Patients withdrawing from the study early because of adverse events should be followed until the adverse event has either resolved or stabilized. Reasons for premature withdrawal should be determined and documented.

In addition, patients will be required to have a structured assessment of post-operative PSA measurements for 3 years. In the first year after prostatectomy, PSA will be measured every 3 months (±1 mo). In the second and third years after prostatectomy, PSA will be measured every 6 months (±2 mo). These PSA measurements may be obtained outside of Johns Hopkins, but the results need to be made available to the study team.

5.6 Duration of Therapy

Participation in this study will be terminated for any of the following reasons listed below:

- the patient decides to withdraw from the study (withdrawal of consent) due to unacceptable toxicities or for any other reason
- the patient completes all of the protocol procedures and follow-up requirements
- there are adverse events that, in the judgment of the investigator, may cause severe or permanent injury or are incompatible with continuation on study
- there are major violations to the study protocol or the patient is noncompliant with treatments, as judged by the investigator
- the patient experiences concurrent illness or a change in his condition that, in the judgment of the investigator, renders him unacceptable for further treatment on study
- the patient dies
- the patient is lost to follow-up
- the study is prematurely terminated for safety or feasibility concerns or other reasons

Patients should be removed from the study when any of the above criteria are met. Because an excessive rate of withdrawals can render the study uninterpretable, unnecessary withdrawal of patients should be avoided if possible. When a patient leaves the study early, the investigator should make every effort to contact the patient and to perform the final follow-up evaluation (even by telephone interview). The reason for removal of a patient from the study, and the date of removal, must be appropriately documented.

Patients will be replaced if they are removed from the study after signing the informed consent but before receiving DUPILUMAB. Patients receiving at least one dose of the study drug will be included in safety analyses, and those also undergoing prostatectomy will be used for the efficacy analyses.

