6.4.3.2 Grade 3 or 4 AEs

Drug administration should be held upon observation of AEs of \geq Grade 3 severity to enable patient management, monitoring of the resolution of the event, and assessment of the relatedness of the event. An AE of \geq Grade 3 that is considered related to DUPILUMAB will result in discontinuation of therapy unless other specified in the protocol. For AEs associated with liver function test abnormalities, drug administration may resume upon resolution of the AE to \leq Grade 1 severity unless more than seven days elapse before return to \leq Grade 2 severity or fourteen days have elapsed from the last dose. In this case, the AE is considered dose limiting, two consecutive doses will have been missed, and study drug administration should be discontinued. Following a single missed dose, the treatment schedule should resume as if no delay had occurred and the patient receive all intended DUPILUMAB doses.

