10.3 Analysis Populations

10.3.1 Intention-to-treat population

All patients who meet eligibility criteria and receive at least one dose of the study drug will be included in the analysis of the primary and secondary endpoints, even if there are subsequent protocol deviations. However, in cases where prostatectomy is not performed or if adequate surgical tissue is not collected, then determination of the secondary endpoints (e.g., CD206, apoptosis/proliferation marker analysis, tissue CD8⁺ T cell analysis) will not be possible. Patients will be replaced if they are removed from the study after signing the informed consent but before receiving the study drug.

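### Section 5.6 does not separate stopping dupilumab from leaving the study, so some dosed men may be removed without the tissue, post-operative and PSA data that Section 10.3.1 relies on

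*Combined protocol and SAP*

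**What the plan says.** Section 5.6 is headed Duration of Therapy, but its opening line concerns the whole study: "Participation in this study will be terminated for any of the following reasons listed below". The list contains:

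- plain study exits: withdrawal of consent, completion, death, loss to follow-up and early termination of the study;
- adverse events that, in the investigator's judgment, "may cause severe or permanent injury or are incompatible with continuation on study";
- major protocol violations, or that "the patient is noncompliant with treatments, as judged by the investigator";
- an illness or change of condition that "renders him unacceptable for further treatment on study".

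Then comes the instruction: "Patients should be removed from the study when any of the above criteria are met". For a man who leaves early, 5.6 asks the investigator to try to reach him and carry out the final follow-up evaluation, by telephone if need be. Replacement is allowed only before the first dose. The last sentence of 5.6 places dosed men in the safety analyses, and those who also have prostatectomy in the efficacy analyses.

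Elsewhere:

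- 10.3.1: eligible men with at least one dose "will be included in the analysis of the primary and secondary endpoints, even if there are subsequent protocol deviations". It adds that tissue endpoints cannot be determined without surgery or adequate tissue.
- 6.4.3.1 and 6.4.3.2: these rules stop drug only. For example, a related event of Grade 3 or higher "will result in discontinuation of therapy unless other specified in the protocol". Neither says whether the man stays on study.
- 5.5: "Patients withdrawing from the study early because of adverse events should be followed until the adverse event has either resolved or stabilized". It also requires three years of post-operative PSA, without saying what applies to men already removed.
- 11.5: safety follow-up is promised for men taken out prematurely, with no content specified.

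**The concern.** Two items in the 5.6 list, noncompliance with treatment and unfitness for further treatment, are reasons about the drug. A third, major violations, is a kind of deviation that 10.3.1 says does not exclude a man from analysis. Under 5.6 all three lead out of the study. No section says that a man who has stopped dupilumab remains on study for tissue collection, the post-operative visits and PSA.

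Removal on these grounds depends on how a man tolerated or adhered to treatment. In a single-arm paired comparison of 20 men, leaving such men out turns the primary result into a result among those who completed the course. The same selection affects the hypothesis that dupilumab does not interfere with prostatectomy. The feasibility rule in 10.1.2 is checked after every patient, but the plan does not say whether removed men count. Tissue not taken at surgery may not be recoverable.

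**Working it through.** **1. The sections side by side**

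| Question | 5.6 | 6.4.3 | 10.3.1 |
|---|---|---|---|
| Man stops drug | Removed if a list item is met | Drug stopped; study status not stated | In the primary and secondary analyses if eligible and dosed |
| Major violation or noncompliance | Removed | Not addressed | Still analysed |
| Data after exit | Final evaluation only | Not addressed | Needs tissue for the primary endpoint |

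The last sentence of 5.6 defines who is analysed. It does not keep anyone on study so that the data are collected. By 3.2, each man already has prostatectomy scheduled at the same hospital, so much of the possible loss is avoidable.

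**2. Safety cover after exit.** Section 7.3 requires all serious events up to 30 days after the last dose, and later ones only if a causal link is suspected. If the last dose is on day 8, 15 or 22, that window closes on day 38 (8 + 30), 45 (15 + 30) or 52 (22 + 30). Surgery is on day 57. For these men the serious-event rule alone does not reach the operation. Sections 7.4, 10.1, 10.3.2 and 11.5 fill part of the gap.

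**3. The plan's power figure.** Inputs from 10.5.2 and 10.5.1: n = 20, effect size 0.67, paired t-test, significance level 0.05. Sidedness is not stated; two-sided is assumed because it reproduces the stated figure.

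Power = P(|T| > t crit), where T is noncentral t with n − 1 degrees of freedom and noncentrality 0.67 × √n. For n = 20 the noncentrality is 0.67 × √20 = 3.00 and power is 81.1%, matching the stated 81% or more. One-sided gives 89.3%.

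**4. Effect of early stoppers.** The documents give no early-stop rate, so k = 0 to 5 of 20 men is an assumption.

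- *Not collected*: n = 20 − k, effect 0.67.
- *Collected, with no M2-TAM change in stoppers* (an extreme assumption): f = k/20, mean = 0.67(1 − f), SD = √(1 + f(1 − f) × 0.67²), n = 20. For k = 4: mean 0.536, SD √(1 + 0.16 × 0.4489) = 1.035, effect 0.518.

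| k | Not collected: n | Power | Collected, no change: power |
|---|---|---|---|
| 0 | 20 | 81.1% | 81.1% |
| 1 | 19 | 78.9% | 76.2% |
| 2 | 18 | 76.4% | 70.8% |
| 3 | 17 | 73.7% | 65.2% |
| 4 | 16 | 70.7% | 59.4% |
| 5 | 15 | 67.5% | 53.5% |

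Without collection, the effect detectable with 81% power rises from 0.67 SD (n = 20) to 0.71 (18), 0.76 (16) and 0.79 (15).

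**5. Selection, same assumption, k = 4.** Mean over all dosed men: 16/20 × 0.67 = 0.536 SD. Mean over men kept: 0.67 SD. Ratio 0.67/0.536 = 1.25.

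**The case against.** The strongest reply is that the protocol does treat stopping drug separately. The dupilumab stopping rules are in 6.4.3, are confined to study drug and do not refer to 5.6. The adverse-event item in 5.6 is worded as continuation on study and left to the investigator. Section 5.6 also asks that unnecessary withdrawals be avoided, and its last sentence uses dosed men who have surgery. Nothing forbids using an early stopper's tissue. Section 10.3.1 accepts that some tissue will be missing. Safety is largely covered: surgical complications are recorded (7.4), formal safety assessment runs to post-operative day 60 (10.1), every dosed man is evaluable for toxicity (10.3.2), and 5.5 and 11.5 add follow-up after early exit.

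Much of this stands, and it rules out two stronger readings. A reader might infer that every reason for stopping dupilumab removes a man from the study; 6.4.3 does not support that. A reader might also infer that the data are certainly lost; the last sentence of 5.6 and 10.3.1 point the other way, so the data are at risk.

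What the reply does not answer is that the treatment-related items and major violations do lead to removal under 5.6, and that no section provides for tissue or serial PSA afterwards. The concession in 10.3.1 covers tissue that cannot be had. It does not justify forgoing tissue from an operation that takes place anyway.

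**Conclusion.** The point holds as a contradiction to be reconciled. Section 5.6 orders removal for reasons that 6.4.3 treats as drug-only or that 10.3.1 treats as analysable deviations, and it states no collection of tissue, post-operative visits or serial PSA after removal. If 5.6 is followed literally, the paired comparison and the feasibility assessment are selected on tolerance and adherence.

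The size cannot be fixed from the documents. Each man lost without tissue costs about 2 to 3 points of power at 0.67 SD. Dosed men are not replaced, and the synopsis counts 20 evaluable men where 4.2 counts 20 in total, so the paired n can fall below 20. The numbers lost are assumptions.

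Two further inferences should be resisted. The 25% overstatement in step 5 is only an illustration: it assumes that 4 of 20 men stop, that they show no M2-TAM change and that all their tissue is lost. No change is an extreme case, since 2.2.1 reports a median of 10 to 13 weeks to undetectable drug after the last steady-state dose, although early stoppers would not have reached steady state. Nor does keeping these men restore power. If they show no change, power is lower with them than without them. The reason to keep them is an unselected comparison consistent with 10.3.1.

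**What to change.** Reconcile 5.6, 6.4.3 and 10.3.1 without altering any criterion for stopping drug:

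- State that coming off drug is not coming off study. Say explicitly that this covers men who meet the treatment-related items or the major-violation item in 5.6.
- State that, unless a man withdraws consent for follow-up, dies or is lost, the following are still collected: study tissue at any prostatectomy he undergoes, day-of-surgery data, day 30 and 60 safety, and scheduled PSA.
- State that dosed, eligible men with tissue are in the primary analysis under 10.3.1, and that their operations count in the feasibility monitoring of 10.1.2.
- Record off-drug and off-study as separate CRF items, each with date and reason.

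The cost is protocol wording and a small CRF change. No procedure is added, because surgery, tissue handling and PSA are already planned. The downside is that under-exposed men may dilute the observed effect and lower power (right-hand column of the table in step 4). The change should be in place before the removal rule is applied to a dosed man.
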